3 STUDY OUTCOMES

Primary outcome measure is time to heal in patients treated with epidermal grafting and SOC vs. SOC alone (**Group 1A** versus **Group 2A** at 6 weeks; and **Group 1A** versus **Group 2B** at 12 weeks).

Secondary outcomes include:

1. Percentage of wounds closed at 6 and 12 weeks.
2. Correlation between protease activity and healing at 4 and 8 weeks.
3. Incidence of adverse events at 12 weeks.
4. Pain reduction between baseline and 12 weeks.
5. Cost-effectiveness (see Appendix 19.4)
6. Cost-benefit (see Appendix 19.4)

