The Treatment Phase (TV1 to TV13) Begins with a series of assessments designed to confirm the subjects’ continued eligibility. Investigators will debride the ulcer. Subjects whose ulcers continue to meet eligibility criteria will then be randomized to one of two groups: (1) One application of epidermal microdome at day zero and standard of care (**Group 1A**) OR (2) standard of care: multi-layer compression (**Group 2A**) (see figure on next page).

During the Treatment Phase, subjects will be evaluated on a weekly basis. Effectiveness evaluations each week will include Investigator assessment of wound healing and measurements of ulcer size using digital photos.

At TV 7, wound assessment will be carried out to evaluate wound healing in **Group 2A**. Subjects in **Group 2A**, whose percentage area reduction (PAR) is <40% will be allowed to have CelluTome™ treatment in addition to continuation of SOC and will constitute **Group 2C**. **Group 2C** will receive a graft at TV7 and TV11. The remainder of **Group 2A** subjects will be termed **Group 2B** subjects. Patient codes will still remain the same to enable tracking continuity.

[figure not shown]
During the Treatment Phase, the wound will be swabbed for protease activity for **Group 1A and 2A/B** subjects: TV1 (In **Group 1A** this will be prior to CelluTome™ application), TV5 and TV9 visits.

Subjects will be evaluated on a weekly basis during the Treatment Phase. Effectiveness evaluations each week will include Investigator assessment of wound healing and measurements of ulcer size using digital planimetry. At TV4 and TV8, Prisma™ is to be applied to the study ulcer for **Groups 1A, 2A, and 2B** subjects. **Group 2C** subjects will receive Prisma™ at TV10. Safety evaluations during the Treatment

CELLUTOME™ IN VENOUS LEG

Phase will consist of adverse event assessments at each visit.

Diagram showing progress of trial and the different subjects groups. Up to 6 weeks from randomization only **Groups 1A and 2A** exist; after 6 weeks, **Groups 1A, 2B, and 2C** exist.

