5.2 INCLUSION CRITERIA

Potential subjects are required to meet all of the following criteria for enrollment into the study and subsequent randomization.

1. At least 18 years old.
2. Ankle Brachial Pressure Index (ABI) > 0.75. Calculations will be made using measurements from both posterior tibial and dorsalis pedis arteries as well as both arms AND/OR Skin Perfusion Pressures (SPP) greater than 30 mmHg OR Biphasic PVR OR TBI > 0.60 OR TCPO₂ > 30mmHg.
3. Presence of a VLU extending through the full thickness of the skin but not down to muscle, tendon, or bone. The largest ulcer will be designated the index ulcer and the only one included in the Study. If other ulcerations are present on the same leg the index ulcer must be 2 cm or greater in distance from the wound edge of the other ulcers.
4. Study ulcer (i.e. current episode of ulceration) had been present for at least one month (30 days) prior to the initial screening visit, and is excluded if it has undergone 12 month of continuous high strength compression therapy over its duration.
5. Study ulcer is a minimum of 2.0 cm² and a maximum of 25 cm² at the TV1 Randomization visit.
6. The target ulcer has been treated with documented full compression for at least 14 days prior to randomization.
7. Ulcer has a clean, granulating base with minimal adherent slough at the TV1 Randomization visit.
8. Females of childbearing potential must be willing to use acceptable methods of contraception (birth control pills, barriers, or abstinence). A urine pregnancy test must be administered during screening, and must be negative, for inclusion into the study.
9. Patient understands and is willing to participate in the clinical study and can comply with weekly visits and the follow-up regimen.
10. Patient has read and signed the IRB/IEC approved Informed Consent Form before screening procedures are undertaken.

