from the mean change in wound area and protease activity between baseline and 4 weeks after 4 weeks of CelluTome™ + SOC (**Group 1A**) versus 4 weeks of SOC (**Group 2A**) will be equal for both groups. Formally, $H_0: r_1 - r_2 = 0$; $H_1: r_1 - r_2 = D_1 \neq 0$, where r_1 is the Pearson correlation coefficient for subjects in **Group 1A** calculated from difference in mean wound area and difference in mean protease activity between baseline and 4 weeks, r_2 is the same specified metric for subjects **Group 2A**, D_1 is the difference ($r_1 - r_2$) assuming the alternative hypothesis, and the statistical test used is Steiger's Z test with the assumption that r will have the same sign for both groups.

H5: Correlation of wound area with protease activity at 8 weeks

The Pearson correlation coefficient (or Spearman's rho in the case of severe non-normality) calculated from the mean change in wound area and protease activity between baseline and 8 weeks after 8 weeks of CelluTome™ + SOC (**Group 1A**) versus 8 weeks of SOC (**Group 2B**) will be equal for both groups. Formally, $H_0: r_1 - r_2 = 0$; $H_1: r_1 - r_2 = D_1 \neq 0$, where r_1 is the Pearson correlation coefficient for subjects in **Group 1A** calculated from difference in mean wound area and difference in mean protease activity between baseline and 8 weeks, r_2 is the same specified metric for subjects in **Group 2B**, D_1 is the difference ($r_1 - r_2$) assuming the alternative hypothesis, and the statistical test used is Steiger's Z test with the assumption that r will have the same sign for both groups.

H6: Reduction in pain score at 12 weeks

The change in mean pain score between baseline and at 12 weeks after 12 weeks of CelluTome™ + SOC (**Group 1A**) versus 12 weeks of SOC (**Group 2B**) will be equal for both groups. Formally, $H_0: \mu_1 - \mu_2 = 0$; $H_1: \mu_1 - \mu_2 = D_1 \neq 0$, where μ_1 is the mean difference in pain score for subjects in **Group 1A** between baseline and 12 weeks, μ_2 is the same specified metric in **Group 2B**, D_1 is the difference ($\mu_1 - \mu_2$) assuming the alternative hypothesis, and the statistical test used is the paired t test if data are normal and the Mann-Whitney test on a non-paired basis if data are non-normal.

H7: Proportion of wounds healed at 12 weeks (Groups 2B versus 2C)

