- Proportion of wounds healed at 12 weeks will be analyzed by chi square (unadjusted); this endpoint may also be analyzed using logistic regression to adjust for the following variables (with and without covariate imputation) if needed:
 - Site
 - Year enrolled (if trial lasts 2 years or more)
 - Treatment group
 - Initial area at randomization (cm²)
 - Initial wound depth (cm)
 - Age of wound at enrollment (days)
 - Smoking status
 - Prior VLU
 - Pain score at randomization

- Patient age
- Gender
- Ethnicity/race
- VCS score
- Diabetes
- Patient on pain medications
- Smoking status
- BMI
- Infection episodes

Note: unadjusted testing for **Group 2C** versus **2B** will be non-inferiority, followed by superiority testing if the former fails and proportion of wounds healed in **Group 2C** is much higher than in **Group 2B**.

- A summary of the incidence of adverse events (count by patient):
 - AE (category)
 - SAE (category; brief description; resolution; should include death)
 - When event happened in relation to start of treatment (days)
 - Associated patient ID, site ID

Incidence of AEs will be analyzed by Mann-Whitney test on a per subject basis.

- Correlation of changes in wound area with changes in protease activity will be first analyzed by calculating the Pearson correlation coefficient for each group or Spearman's rho if data are grossly non-normal. For each subject the change in protease activity is calculated by subtraction of the value at 4 or 8 weeks from the value at baseline; reduction in wound area is calculated similarly. Differences in r will be analyzed using Steiger's Z test with the assumption that r will have the same sign for both groups. If significant differences are found between groups, further analysis using GLM doubly multivariate repeated measures (change in wound area and protease activity between baseline and 4 and 8 weeks) to adjust for the following variables (with and without covariate imputation) may be undertaken (ordinal re-categorization will be done if data are severely non-normal):
 - Site
 - Year enrolled (if trial lasts 2 years or more)
 - Treatment group
 - Initial area at randomization (cm²)
 - Initial wound depth (cm)
 - Age of wound at enrollment (days)
 - Smoking status
 - Prior VLU
 - Pain score at randomization
 - Patient age
 - Gender
 - Ethnicity/race
 - VCS score

CELLUTOME™ IN VENOUS LEG

- Diabetes
 - Patient on pain medications
 - Smoking status
 - BMI
 - Infection episodes

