- Reduction in pain score (baseline – Week 12) will be analyzed by paired t test if the dependent variable data are not grossly non-normal or the Mann-Whitney test if they are grossly non-normal (unadjusted).

To create the flow chart, the following numbers will be required for each group: eligible (n), screened (n), screen failure (n, with categorical reasons), randomized (n), completed 12 weeks study (n), withdrawals or lost to follow-up after randomization (n, with categorical reasons).

These variables are required for the final analysis:

- Site ID (alphanumeric)
- Patient ID (alphanumeric)
- Year enrolled (numeric; date, year only)
- Group assignment (nominal factor, [1A, 2A, 2B, 2C]; note: subjects in 2A can also have 2B or 2C assignments as well)
- Lost to follow up (binomial factor [1,0; 1 = yes]; estimated date lost to follow-up; associated patient ID; categorical reason for lost to follow-up)
- Death during study (binomial factor [1,0; 1 = yes]; estimated date when death occurred)
- Gender (nominal factor [1, 0; male = 1])
- Subject age at S1 (continuous variable with breakpoint at > 90 years if > 90)
- Ethnicity/race (multinomial factor)
- Smoking status at S1 (ordinal factor: [1, 2, 3; never, ever, current])
- Wound count (Poisson distribution variable; count of VLU at patient level at randomization)
- Index Ulcer location (multinomial factor)
- Prior VLU at S1 (binomial factor [1,0; 1 = yes])
- Wound age at S1 (continuous variable, days; S1)
- Pain score (continuous variable, 0-10, TV1 and 13)
- VCS score at S1 (continuous variable, 0-24)
- BMI at S1 (continuous variable)
- Diabetes at S1 (nominal factor [1, 0; yes = 1])
- Subject on pain medication at S1 (nominal factor [1, 0; yes = 1])
- Wound area (continuous variable, cm²; weekly, weeks TV1-13)
- Wound depth (continuous variable, cm; weekly, weeks TV1-13)
- Outcome healed at 12 weeks (binomial factor, [1,0; 1 = yes])
- Time to heal (continuous variable, 0-84, days after randomization for healed wounds)
- Initial wound healed within 12 weeks and confirmed closed about 2 weeks later (binomial, [1,0; 1 = yes])
- Ulcer recurrence by 12 weeks (binomial factor, [1,0; 1 = yes]; estimated days after randomization when event occurred)
- Infection episode (Poisson variable, weeks TV1-13)
- AE (Poisson distribution variable, count at patient level; date of onset)

CELLUTOME™ IN VENOUS LEG

- TEAE (Poisson distribution variable, count at patient level for each of 4 categories; date of onset)

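### H4 and H5 correlate protease change with cm² of ulcer area lost, unadjusted for a starting area of 2 to 25 cm², which weakens each group's correlation with healing

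*Combined protocol and SAP*

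**What the plan says.** The secondary outcome in Section 3 is "Correlation between protease activity and healing at 4 and 8 weeks", and the synopsis lists the same endpoint. In Section 9.2, H4 and H5 are titled as correlations of wound area with protease activity. For H4 the coefficient is "calculated from difference in mean wound area and difference in mean protease activity between baseline and 4 weeks"; H5 uses the same construction at 8 weeks.

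Section 9.7, item 6, makes this a per-subject calculation. Protease change is obtained by "subtraction of the value at 4 or 8 weeks from the value at baseline; reduction in wound area is calculated similarly". Nothing is divided by the baseline value. The variable list in the same section records "Wound area (continuous variable, cm²; weekly, weeks TV1-13" and contains no percentage measure. The analysis starts by "calculating the Pearson correlation coefficient for each group or Spearman's rho if data are grossly non-normal", and then: "Differences in r will be analyzed using Steiger's Z test with the assumption that r will have the same sign for both groups".

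On starting size, Section 5.2 requires: "Study ulcer is a minimum of 2.0 cm² and a maximum of 25 cm² at the TV1 Randomization visit". On grading partial healing, Section 4 applies a relative rule at TV7 to control subjects "whose percentage area reduction (PAR) is <40% will be allowed to have CelluTome™ treatment in addition to continuation of SOC". Sections 4 and 5.3 also exclude ulcers that shrink by more than 40% during the run-in.

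**The concern.** An absolute loss in cm² mixes two things: how large the ulcer was and what share of it closed. Eligibility permits a 12.5-fold range in the first (25 / 2). A large ulcer that has barely changed can outscore a small one that has nearly closed. The part of the score that comes from starting size is noise for the question of whether falling protease activity accompanies healing.

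Two consequences follow. If protease change is unrelated to ulcer size, each group's r is pulled toward zero and the comparison of r between groups loses power. If protease change does vary with ulcer size, r can also move for a reason that has nothing to do with relative healing.

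**Working it through.** **No plan figure to reproduce.** The documents give no expected r, SD or power for H4 or H5, and no distribution of baseline area. Everything below except step 1 rests on stated assumptions.

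**Step 1: scale (arithmetic only).** Score D = A × P, where A is area at TV1 and P is the fractional reduction.
- 2 cm² ulcer reduced by 90%: 2 × 0.90 = 1.8.
- 25 cm² ulcer reduced by 10%: 25 × 0.10 = 2.5, which ranks higher.
- 25 cm² ulcer reduced by 40%: 10, five times the highest score a 2 cm² ulcer can reach (2).

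**Step 2: how much of the score is size.** Assume A and P are independent. Then:
- SD(D)² = E[A²]E[P²] − (E[A]E[P])²
- r(P,D) = E[A]·SD(P)/SD(D)
- r(A,D) = E[P]·SD(A)/SD(D)

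Example: A uniform on 2-25, so mean 13.5, SD 23/√12 = 6.64 and E[A²] = 226.3. P has mean 0.39 and SD 0.38 (a normal with mean 0.4 and SD 0.4, capped at 1), so E[P²] = 0.2965.
- SD(D)² = 226.3 × 0.2965 − (13.5 × 0.39)² = 67.1 − 27.7 = 39.4, so SD(D) = 6.28.
- r(P,D) = 13.5 × 0.38 / 6.28 = 0.82.
- r(A,D) = 0.39 × 6.64 / 6.28 = 0.41.

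Monte Carlo (1,000,000 subjects per scenario) gave the same values. It covered 18 scenarios: area uniform, log-uniform or truncated log-normal on 2-25 cm², with nominal P mean 0.3-0.7 and SD 0.3-0.5. Across them r(A,D) ran from 0.26 to 0.83, so starting size explains 7% to 69% of the variance of cm² lost, and more than half in 5 of 18. The rank correlation ran from 0.27 to 0.83, so Spearman's rho does not remove the dependence.

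**Step 3: effect on r within a group.** If protease change X is related to P but not to A, r(X,D) = r(X,P) × r(P,D). With a true r(X,P) of 0.40:

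| Area distribution | Nominal P mean/SD | r(P,D) | r on cm² lost | r on PAR |
|---|---|---|---|---|
| Uniform | 0.4/0.4 | 0.82 | 0.33 | 0.40 |
| Uniform | 0.6/0.3 | 0.65 | 0.26 | 0.40 |
| Log-uniform | 0.4/0.4 | 0.71 | 0.28 | 0.40 |
| Log-uniform | 0.6/0.3 | 0.52 | 0.21 | 0.40 |

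A true zero stays zero. Only if X is also given a correlation of 0.2-0.4 with size does a true zero become 0.08-0.31 and a true 0.40 become 0.36-0.54.

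**Step 4: effect on the between-group test.** Use Fisher's z for two independent groups of 112 and 113 (Section 9.3), with no missing data: SE = √(1/109 + 1/110) = 0.135.
- *Power, assumed true r of 0.5 vs 0.2.* Undistorted: (0.549 − 0.203)/0.135 = 2.57, power 73%. Step 3 gives shrinkage factors of 0.21/0.40 = 0.525 to 0.33/0.40 = 0.825. At 0.825 the pair is 0.41 vs 0.17 and power is 52%; at 0.525 it is 0.26 vs 0.11 and power is 23%.
- *Shift under equal true r.* Give both groups a true 0.40, but let one heal at nominal 0.4/0.4 and the other at 0.6/0.3. Step 3 gives 0.33 vs 0.26 (uniform) or 0.28 vs 0.21 (log-uniform). The latter is (0.288 − 0.213)/0.135 = 0.55 SE, which would raise a 5% false-positive rate to about 9%.

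**Step 5: the remedies in the same scenarios.** PAR recovers 0.40 as 0.40 and 0 as 0.00. Keeping cm² lost and partialling out TV1 area gives 0.33-0.39 and 0.00.

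**The case against.** The strongest reply has five parts.

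- **What is tested.** H4 and H5 test a difference in r, not r itself. For H4, randomization balances starting size in expectation, so much of the distortion is common to both groups, and the illustrated shift is small beside sampling error. This stands, and it limits the harm mainly to power. It carries less weight for H5, where Group 2B is a subset chosen after randomization by its week-6 area reduction.
- **Initial area is already a covariate.** Section 9.7 lists it in the follow-on GLM. But that model is optional and is reached only after a significant between-group difference, so it cannot protect the test that opens the way to it.
- **The hypotheses measure what their titles say.** Section 9.2 speaks of wound area, so the mismatch is only with the word healing in the synopsis and Section 3. That is correct, and it is the extent of the mismatch.
- **Closed ulcers may not be swabbed.** Section 6.3 waives further procedures at a visit where the ulcer is healed, so a closed small ulcer may enter only by carrying an earlier value forward. The example in step 1 therefore uses a 90% reduction.
- **The simulation favors PAR.** It assumes that PAR is independent of size and is what protease relates to. This is fair, and it is why the partial correlation is offered as an equal alternative.

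A reader might infer that the protease-healing correlation would largely reflect starting size. The documents do not support that. Size enters r, as opposed to diluting it, only if protease change is itself related to size. No section reports such a relation, and the swab procedure in Appendix 19.7 states no scaling with ulcer area. A reader might also infer that the protocol judges healing by percentage everywhere else. It does not: Section 8.7.3 defines healing by closure, H1 and H2 use closure, and the deterioration rule in Section 9.6 uses any increase in area.

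**Conclusion.** The point holds as a limited weakness in two secondary analyses. H4 and H5 use absolute cm² lost with no adjustment for starting area, although the outcome is described as healing and the protocol grades partial healing in relative terms. Under the assumed distributions a true within-group correlation of 0.40 is reduced to about 0.21-0.33. The main cost is power for the between-group comparison: 73% falls to 23-52% in the illustration. A modest shift, about 0.55 SE in one assumed scenario, can arise when the groups heal differently. Confounding by size is possible but not established.

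The direction of the attenuation follows from the definition of the score when area and relative healing are independent. Its size depends on the area distribution, the healing distribution and that independence, none of which the documents supply. The 2-25 cm² range is an eligibility limit, not an observed spread. The group sizes of 112 and 113 are also optimistic, particularly for H5: Section 5.1 expects 30% of Group 2A to leave for Group 2C, so about 113 × 0.70 = 79 would remain before dropout.

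**What to change.** In Section 9.2 (H4 and H5) and Section 9.7 (item 6, including the follow-on GLM), define the wound variable for each subject as

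PAR = 100 × (area at TV1 − area at week 4 or 8) / area at TV1,

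and correlate it with that subject's protease change. Specify Spearman's rho if enlarging ulcers give extreme negative values. Add PAR at TV5 and TV9 to the list of analysis variables. PAR is defined for a closed ulcer (100%), whereas a log area ratio would need a special rule at zero area.

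Alternatively, keep the cm² change and use a partial correlation given area at TV1 in each group.

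Either option is a change of SAP wording only, since areas are already collected weekly. The small downside of PAR is a skewed lower tail from ulcers that enlarge. Neither option addresses the post-randomization selection of Group 2B in H5.

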	
CelluTome™ system at TV1, TV5 and TV9, visits plus SOC (multi-layer compression) (Group 1A) (2) SOC alone (Group 2A).
 
At TV 7, wound assessment will be carried out to evaluate wound healing in Group 2A. Subjects in Group 2A, whose percentage area reduction (PAR) is <40% will be allowed to have CelluTome™ treatment in addition to continuation of SOC and will constitute Group 2C. Group 2C subjects will receive a graft at TV7 and TV11. The remainder of Group 2A subjects will be termed Group 2B subjects. Patient codes will still remain the same to enable tracking continuity.
 
During the Treatment Phase, the wound will be swabbed for protease activity for Group 1A and 2A/B subjects: TV1 (In Group 1A this will be prior to CelluTome™ application), TV5 and TV9 visits.
 
Subjects will be evaluated on a weekly basis during the Treatment Phase. Effectiveness evaluations each week will include Investigator assessment of wound healing and measurements of ulcer size using digital planimetry. At TV4 and TV8, Prisma™ is to be applied to the study ulcer for Group 1A, 2A, and 2B subjects. Group 2C subjects will receive Prisma™ at TV10. Safety evaluations during the Treatment Phase will consist of adverse event assessments at each visit.

Dosage and Frequency of Administration
	
Epidermal grafting will be applied up to three times in Group 1A: TV1, TV5 and TV9. Group 2C subjects will receive up to two grafts: TV7 and TV11.

Duration of Study
	
A run-in period of 2 weeks followed by 12 weeks of active treatment.

Statistical Methods, Power, and Sample Size Calculations
	
Please see the Statistical Analysis Plan in the protocol.

Protease Levels
	
Absolute values of inflammatory proteases (Neutrophil elastase, MMP 8 and 9) will be measured at S1 before application of Prisma™, day 0 before application of Epidermal grafts and week 4 and 8 visits thereafter to determine the effect of protease levels on graft success for Group 1A and 2A/B subjects. The results will be blinded to the Investigators.

Key Words
	
Epidermal Grafts Chronic Wounds Clinical Trial Venous Leg ulcer Protease levels in chronic wounds

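### The protease correlation is estimated in each arm but formally tested only for a difference between arms, so the stated secondary objective gets no test or confidence interval.

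*Combined protocol and SAP*

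**What the plan says.** The synopsis lists the correlation between protease activity and healing as a secondary objective. Section 3 states the outcome as "Correlation between protease activity and healing at 4 and 8 weeks". The Protease Levels row of the synopsis says that neutrophil elastase, MMP 8 and MMP 9 are measured at S1, at day 0 before grafting, and at weeks 4 and 8, "to determine the effect of protease levels on graft success for Group 1A and 2A/B subjects".

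Section 9.2 turns this into H4 (week 4, Group 1A against 2A) and H5 (week 8, Group 1A against 2B). In both, the null hypothesis is r1 − r2 = 0, and "the statistical test used is Steiger's Z test with the assumption that r will have the same sign for both groups".

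Section 9.7, item 6, says that the correlation of change in wound area with change in protease activity "will be first analyzed by calculating the Pearson correlation coefficient for each group or Spearman's rho if data are grossly non-normal". The between-group step follows: "Differences in r will be analyzed using" Steiger's Z. Modelling comes last and is conditional: "If significant differences are found between groups, further analysis using GLM doubly multivariate repeated measures", which the plan permits but does not require.

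Protease is not among the covariates of the Cox or logistic models in section 9.7, nor in that section's list of variables required for the final analysis.

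**The concern.** The objective asks whether protease activity goes with healing. The hypothesis asks whether grafting changes that relation. The second question is legitimate, but its answer does not settle the first. A marker that tracks healing equally well in both arms satisfies the H4 and H5 null, so the expected formal result is non-significant. Conversely, H4 can reject when one arm has no correlation at all.

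The rest of the plan does not fill the gap. The GLM is reached only through a significant between-arm difference, and it treats change in protease as an outcome beside change in area, not as a predictor. Both correlated quantities are changes over the same interval, so a fall in protease could simply accompany wound shrinkage. The S1 and TV1 levels enter only as the starting point of a change score, and no level measured before the graft is related to later closure or time to heal.

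At stake is the inferential value of a secondary endpoint for which swabs are taken at four time points. A positive biomarker statement would have to rest on an unplanned test.

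**Working it through.** **1. The plan's own power figure.** The only one is 86.1% for time to heal (section 9.3: 113 control and 112 treated, hazard ratio 1.74, control healing 0.5 at 12 weeks, dropout 0.033 and 0.0083 per week). A Lakatos-type calculation gives 85.7% with about 123 events; on those events Schoenfeld's formula gives 86.7% and Freedman's 85.0%. The figure reproduces within 2 points, so its inputs can be reused below. No power is given for H4 or H5.

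**2. Objective and analysis side by side.**

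| | Question | Null |
|---|---|---|
| Synopsis and section 3 | Is protease activity correlated with healing? | r = 0 |
| H4, H5 and section 9.7 | Does the correlation differ between arms? | r1 − r2 = 0 |
| Synopsis, Protease Levels | Does the protease level affect graft success? | none written |

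Section 9.1.1 promises hypothesis testing for secondary endpoints, but the only hypothesis written for this one is the second row.

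**3. Behaviour of the planned comparison.** For independent groups, z = (atanh r1 − atanh r2) / √(1/(n1−3) + 1/(n2−3)). If the true r is equal in both arms, the numerator has expectation zero, and the rejection probability is 0.05 at r = 0.2, 0.3, 0.4 or 0.5 alike.

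**4. How many pairs there may be.** Under section 6.3 a healed ulcer needs no further procedures at that visit, and under section 6.4 the subject has then completed the study. New swabs therefore come mainly from open ulcers. Assume constant hazards with the section 9.3 inputs, 30% of Group 2A switching to 2C (section 5.1), all switchers unhealed, and no dropout:

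- Week 4, Group 1A: 112 × 0.5^(1.74 × 4/12) = 112 × 0.669 ≈ 75
- Week 4, Group 2A: 113 × 0.5^(4/12) = 113 × 0.794 ≈ 90
- Week 8, Group 1A: 112 × 0.5^(1.74 × 8/12) = 112 × 0.448 ≈ 50
- Week 8, Group 2B: 113 × 0.5^(8/12) − 0.30 × 113 = 71.2 − 33.9 ≈ 37

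**5. Power of a pooled within-arm test of r = 0.** The documents give no value of r, so it is assumed. The standardised effect is atanh(r) × √((n1−3) + (n2−3)), compared with 1.96 (two-sided 0.05). At r = 0.30, atanh(r) = 0.3095.

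- Week 4: 0.3095 × √(72 + 87) = 3.90, power about 97%
- Week 8: 0.3095 × √(47 + 34) = 2.79, power about 80%

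| Assumed common r | Planned comparison | Pooled test, week 4 | Pooled test, week 8 |
|---|---|---|---|
| 0.20 | 5% | 72% | 45% |
| 0.30 | 5% | 97% | 80% |
| 0.40 | 5% | over 99% | 97% |

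**6. Multiplicity.** Section 9.7 applies Hochberg's procedure. At its strictest step for the eight listed hypotheses, alpha is 0.05/8 = 0.00625 (critical value 2.73). Power at r = 0.30 is then about 88% at week 4 and 52% at week 8.

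**The case against.** The strongest reply is that the objective is partly met. Section 9.7 calculates r in each group, so a marker common to both arms would show as two similar coefficients. This stands. A reader might infer that the association is never examined; the documents do not support that. It is estimated, but without a test or an interval.

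A reader might also take the effect of protease on graft success to be the trial's formal biomarker question. The documents do not support that either. The phrase occurs in one synopsis row, is not defined, is not a listed objective, endpoint or hypothesis, and is applied there also to Groups 2A/B, whose subjects receive no graft. The mismatch with that stated purpose is real, but a model to address it belongs among the exploratory analyses.

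Third, the power gain is easy to overstate. With 80 to 100 pairs per arm at both visits, the pooled test would have 97% to 99% power at r = 0.30. That ignores closed ulcers and switching, which bring week 8 down to about 80%. LOCF for secondary endpoints could supply more pairs, but they would be carried-forward values and not new samples.

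Fourth, the 5% was derived with Fisher's z, whereas the plan names Steiger's Z, a test for dependent correlations. The 5% is the nominal size of any valid test under a true null; it is not a measured loss of power. Finally, a test of the common correlation still concerns concurrent changes, so it would establish association and not prediction. Both points stand. They limit the claim without removing the mismatch between objective and hypothesis.

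**Conclusion.** The point holds as a mismatch between a stated objective and the hypothesis written for it. The protease–healing correlation is estimated descriptively by arm but is not tested against zero or given a confidence interval. The adjusted analysis is optional and depends on an unrelated result, and no pre-graft level is related to later healing.

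That equal correlations leave the planned comparison at about 5% follows from the null itself and needs no assumption about r or n. The contrasting 97% (week 4) and 80% (week 8) rest on an assumed r of 0.30, constant hazards, the plan's healing and switching rates, pairs from open ulcers only, no dropout and no multiplicity adjustment. They illustrate scale and are not predictions.

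The primary analysis is unaffected. The change should be made because the data are already to be collected and the gap lies in the formal hypothesis.

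**What to change.** - Restate H4 and H5 so that the formal test is of the common within-arm correlation against zero, adjusted for arm, with confidence intervals by arm and pooled.
- Keep r1 − r2 as exploratory, using the Fisher z comparison for independent groups.
- Remove the condition that the adjusted analysis follows only a significant between-arm difference.
- Add, as exploratory, a Cox model of time to heal on the TV1 pre-graft protease level, with arm and a level-by-arm interaction. Fit it for each of the three proteases, or for one marker named in advance.
- Add protease values to the section 9.7 list of variables required for the final analysis.

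The cost is SAP wording and one or two extra models, with no new samples or visits. The downside is some multiplicity across the three proteases, which naming one marker in advance would limit. The change should be made before database lock.
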